#### 4.3 Secondary endpoints

The secondary endpoints are:

1. Description of patient characteristics by treatment group at V0 (demographics, clinical characteristics, history of CVD, treatment history, specific comorbidities) and description of risk factors and treatment characteristics per visit (type of treatment [initial referral from General Practitioner (GP) and whether they actually received the treatment], concomitant treatment, compliance with conservative treatment).
2. Proportion of patients who received an intervention as secondary/add-on treatment to conservative treatment (in the conservative treatment group). Proportion of patients who received a re-intervention (in the invasive treatment group) and number of re-interventions. Time to secondary/add-on intervention or re-intervention.
3. The change in the GIS of CIVIQ-20 over time from V0 to each follow-up visit.
4. The change in the clinical part of the CEAP classification over time from V0 to each follow-up visit.
5. The change in the rVCSS over time from V0 to each follow-up visit.
6. The change in the symptomatology over time from V0 to each follow-up visit.
7. The change in satisfaction score over time from V1 to each follow-up visit.
8. The change in CIVIQ-20, CEAP, rVCSS, symptomatology and satisfaction scores in patients who received an intervention as secondary/add-on treatment to conservative treatment.
9. Number and proportion of patients with Adverse Events (AEs).

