#### 4.4 Study Design

This study is an observational, prospective, multicentre study to assess the effectiveness of conservative and invasive treatments of patients with CVD in Belgium. The inclusion period of the study will last 6 months. Patients will be followed until 2 years after inclusion into the study. The study is expected to start in Jan-2024 and be completed by Jul-2026.

During the inclusion period, after confirmation of eligibility, patients with CVD diagnosed by the GP and looking for a treatment will be invited to participate in the study. About 120 GPs will be included in the study.

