#### **4.4.2 Study setting**

The GP examines the patient and makes the diagnosis of CVD, based on clinical signs and symptoms. Patients who receive a diagnosis of CVD according to international guidelines who require conservative or invasive treatment can be included in the study. Duplex ultrasound or any other specific examination is not required to make the diagnosis, but could be done if needed according to routine clinical practice and recommendations. Each participating GP (120 GPs) will select approximately between 10 and 15 patients with CVD.

During the inclusion visit (V0), a treatment strategy will be proposed to the patient with confirmed CVD by the GP. The treatment can be conservative or invasive, depending on the severity of the disease. Patients awaiting invasive treatment may receive conservative treatment to alleviate symptoms. The choice of treatment modality is left to the discretion of the treating physician, in agreement with the patient and according to local policies. As this is an observational study, there will be no interference in the choice of treatment, and no restrictions will be imposed.

Commonly proposed conservative treatment options include compression therapy, and oral or topical venoactive drugs. If the GP decides that the patient needs an invasive treatment, then the patient will be referred to a venous centre. The specialist to whom the patient is referred, chooses the type of invasive treatment, as done in standard clinical care. The specialist may also prescribe conservative treatment to the patient, either while awaiting invasive treatment or in case invasive treatment is not deemed necessary.

[figure not shown]
Patients and their GP may decide to switch at any time between conservative treatments or to undergo an intervention as secondary/add-on treatment to conservative treatment.

Baseline data will be collected by the GP on the day of the V0. Follow-up visits, which are expected to take place within the scope of routine clinical practice, will be organized by the GP at defined timepoints after the V0: at 6 weeks, 12 weeks, 6 months, 12 months and 24 months of follow-up (V1-V5).

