## 8. Assessment of safety

### 8.1 Specification, timing and recording of safety parameters

According to the International Conference on Harmonisation (ICH), an **AE** is any untoward medical occurrence in a subject or clinical investigation subject administered a pharmaceutical product and which does not necessarily have a causal relationship with this treatment. An AE can therefore be any unfavourable and unintended sign (including an abnormal laboratory finding), symptom or disease temporally associated with the use of a medicinal (investigational) product, whether or not related to the medicinal (investigational) product. Worsening of a pre-existing condition during the study must also be recorded as an AE.

A Treatment Emergent Adverse Event (**TEAE**) is defined as any event not present prior to the initiation of the treatments or any event already present that worsens in either intensity or frequency following exposure to the treatments.

A Serious Adverse Event (**SAE**) is defined as any untoward medical occurrence that:

- Results in death,
- Is life-threatening (the term 'life-threatening' refers to an event in which the subject was at risk of death at the time of the event; it does not refer to an event which hypothetically might have caused death if it were more severe),
- Requires inpatient hospitalisation or prolongation of existing hospitalisation,
- Results in persistent or significant disability or incapacity,
- Is a congenital anomaly or birth defect.

Pharmacovigilance data include any unintended or adverse event associated with the use of a medicinal product in humans, whether or not considered drug related, including the following special situations (situations where no AE occurred but information needs to be collected):

- Exposure during pregnancy (maternal and/or transmission of a medicinal product via semen following paternal exposure) or breastfeeding,
- Overdose, abuse, misuse, off label use, medication error, occupational exposure,
- Drug-drug or drug-food interactions,
- Any suspected transmission via a medicinal product of an infectious agent,
- Unintended therapeutic benefit,
- Lack of efficacy.

AEs and special situations will be assessed during each follow-up visit and recorded in the eCRF.

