### **9.2 Sample size**

Considering a Minimum Clinically Important Difference (MCID) of 5 points before/after treatment for the primary endpoint (CIVIQ-20 GIS), a default correlation of 0.5, and with an expected drop-out of 60% of patients in the conservative group and 25% in the invasive group, we propose the recruitment of 1650 patients (safe margin), to finally include minimally 1590 patients (power 90%).

Each investigator (120 GPs) will recruit approximately between 10 and 15 consecutive patients.

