### **Secondary endpoints**

The analyses will be conducted in the AS, overall and by treatment group (conservative group, invasive group). Descriptive statistics and within-group comparative analyses could be done by subgroup of conservative treatment (venoactive drugs, compression, combination of both), or by subgroup of invasive treatment (sclerotherapy, foam sclerotherapy, surgery, thermal ablation (laser or radiofrequency), non-thermal ablation, and venous stenting), if relevant.

Descriptive statistics will be provided for patient characteristics at V0 (in terms of demographics, profession, clinical characteristics, personal and family history of CVD, treatment history, specific comorbidities), risk factors, concomitant treatment and description of treatment characteristics per visit in terms of type of treatment (initial referral from GP and whether they actually received the treatment), concomitant treatment, compliance (for conservative treatment group only).

The proportion of patients who received an intervention as secondary/add-on treatment to conservative treatment (in the conservative treatment group) and the proportion of patients who received a re-intervention (in the invasive treatment group) and number of re-interventions will be provided. If there is enough recurrence (minimum 20% of concerned patients), a Kaplan-Meier analysis could be considered. Time to event will be calculated from the start date of conservative treatment to the date of the secondary/add-on intervention in the conservative treatment group.

Time-to-re-intervention will be calculated from the date of the intervention to the date of the re-intervention in the invasive treatment group.

Patients who will reach the end of the study without receiving an intervention (in the conservative group) or a re-intervention (in the invasive treatment group) will have the time to event censored at the date of treatment discontinuation for any other cause (in the conservative group) or at the date of the end of the study if study ended (in conservative and invasive treatment group).

The change in the CIVIQ-20 GIS over time from V0 to each follow-up visit will be evaluated with the same methods as the primary endpoint.

The change in the clinical part of the CEAP classification over time from V0 to each follow-up visit will be described.

The change in the rVCSS over time from V0 to each follow-up visit will be evaluated with the same methods as the primary endpoint.

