The change in the symptomatology over time from V0 to each follow-up visit will be evaluated with the same methods as the primary endpoints.

The satisfaction score over time from V1 to each follow-up visit will be described as a quantitative variable.

Number and proportion of patients with AEs will be described.

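### Safety is described only as a crude proportion of patients with AEs by group, which can make the conservative group look safer if the expected 60% vs 25% drop-out shortens AE observation

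*Protocol*

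**What the plan says.** Secondary objective 9 is the safety of the treatments. Endpoint 9 in Section 4.3 is a count and proportion of patients with AEs. The whole analysis in Section 9.3.3 (Secondary endpoints) is: "Number and proportion of patients with AEs will be described". The same section sets the population and layout for all secondary endpoints: "The analyses will be conducted in the AS, overall and by treatment group (conservative group, invasive group").

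These provisions bear on that figure:

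- **Follow-up.** Section 4.4: "Patients will be followed until 2 years after inclusion into the study". Under Section 8.1, AEs are assessed at each follow-up visit.
- **Drop-out.** Section 9.2 sizes the study "with an expected drop-out of 60% of patients in the conservative group and 25% in the invasive group". No time frame is given.
- **Analysis Set.** Section 9.3.2 requires only one attended visit among V1, V2 and V3.
- **Treatment changes.** Section 4.4.2: "Patients and their GP may decide to switch at any time between conservative treatments or to undergo an intervention as secondary/add-on treatment to conservative treatment". The same section lets patients who are waiting for an intervention take conservative treatment.
- **Treatment-emergent AE.** Section 8.1 says that it "is defined as any event not present prior to the initiation of the treatments or any event already present that worsens" after exposure. Neither endpoint 9 nor its analysis uses this definition.
- **Data collected.** Sections 6.1 and 8.2 and the notes to Table 1 provide AE start dates, treatment start and intervention dates, dates of add-on and re-interventions, and the investigator's judgement of relationship to treatment.

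**The concern.** A crude proportion treats a patient watched for a few weeks like one watched for two years. It is a fair summary when groups are observed for similar times. Here the protocol itself expects the conservative group to lose more than twice the share of patients that the invasive group loses. A patient who stops attending stops contributing AEs but, after one early visit, stays in the denominator. The group that loses more patients then tends to show the lower percentage, whatever the true AE risk.

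A second, less certain issue is that the treatment group may not identify the treatment a patient was on when an AE began. A conservative patient can have an add-on intervention, and an invasive patient can have an AE before the procedure.

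At stake is how the published safety table will be read. Two percentages side by side under a safety objective invite comparison even when no test is attached.

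**Working it through.** The protocol gives no figure for the safety endpoint, so there is none to reproduce. The check asks what the crude proportion would show if both groups had the same AE hazard.

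**Inputs from the protocol:** drop-out d = 0.60 (conservative) and 0.25 (invasive), Section 9.2; planned follow-up 2 years, Section 4.4.

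**Assumptions, not in the protocol:** constant hazard h of first AE, the same in both groups, from 0.1 to 0.6 per patient-year; drop-out ends AE observation and is either uniform over 24 months or all at week 12 (12/52 = 0.231 years); all drop-outs stay in the Analysis Set.

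**Formula.** Expected crude proportion = (1 − d) × F + d × G, where

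- F = 1 − exp(−2h), the risk of a first AE over 2 years
- G = 1 − F/(2h) for uniform drop-out, or G = 1 − exp(−0.231h) for drop-out at week 12

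The gap between groups is therefore (0.60 − 0.25) × (F − G) = 0.35 × (F − G).

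**Mean planned observation.** Uniform: 0.40 × 2 + 0.60 × 1 = 1.40 years against 0.75 × 2 + 0.25 × 1 = 1.75 years. Week 12: 0.40 × 2 + 0.60 × 0.231 = 0.94 against 0.75 × 2 + 0.25 × 0.231 = 1.56.

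**Worked case, h = 0.3.** F = 1 − exp(−0.6) = 0.451.

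- Uniform: G = 1 − 0.451/0.6 = 0.248. Conservative 0.40 × 0.451 + 0.60 × 0.248 = 0.329; invasive 0.75 × 0.451 + 0.25 × 0.248 = 0.400.
- Week 12: G = 0.067. Conservative 0.40 × 0.451 + 0.60 × 0.067 = 0.221; invasive 0.75 × 0.451 + 0.25 × 0.067 = 0.355.

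| Hazard per year | Drop-out | Conservative | Invasive | Gap (points) |
|---|---|---|---|---|
| 0.1 | uniform | 12.9% | 15.9% | 3 |
| 0.1 | week 12 | 8.6% | 14.2% | 6 |
| 0.3 | uniform | 32.9% | 40.0% | 7 |
| 0.3 | week 12 | 22.1% | 35.5% | 13 |
| 0.6 | uniform | 53.0% | 62.9% | 10 |
| 0.6 | week 12 | 35.7% | 55.6% | 20 |

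With exponential instead of uniform drop-out over 24 months, h = 0.3 gives 30.9% vs 39.8%, so the result does not hang on the exact shape.

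**Effect of the Analysis Set rule** (week 12, h = 0.3, F − G = 0.384). Suppose the same share of drop-outs in each group never attends V1, V2 or V3 and so leaves the denominator.

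- None: gap 0.35 × 0.384 = 0.134.
- Half: the remaining drop-out fractions are 0.30/0.70 = 0.429 and 0.125/0.875 = 0.143. Gap (0.429 − 0.143) × 0.384 = 0.110, about 11 points.
- All: only completers remain, with equal follow-up. Gap 0.

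**What the remedy recovers.** Under the same assumptions, with censoring unrelated to AE risk, Kaplan-Meier incidence at 24 months is F in both groups (45.1% at h = 0.3; 18.1% at h = 0.1), and the rate of first AEs is 30 or 10 per 100 patient-years in both.

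**Treatment at onset.** If 5% to 20% of conservative patients had an add-on intervention carrying a 10% to 30% procedural AE risk (all assumed), between 0.05 × 0.10 = 0.5% and 0.20 × 0.30 = 6% of the group would have such an AE. If the wait for an intervention were 6 to 26 weeks at h = 0.1 to 0.3, then 1 − exp(−0.1 × 6/52) = 1.1% to 1 − exp(−0.3 × 26/52) = 13.9% of invasive patients would have an AE before it. These act on different groups, and the net effect cannot be derived from the protocol.

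**The case against.** Five points can be made for the plan.

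1. **The analysis is descriptive.** Section 9.3.3 calls the analyses mainly descriptive, its tests are within-group, and none is stated for safety between groups. This stands. A reader might infer that the study will declare a false safety difference; the protocol does not support that.

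2. **The drop-out figures are being stretched.** They are expectations, given only in the sample-size section for a 12-week endpoint and without a time frame. Section 4.4.2 also allows visits not to take place, so a patient lost to the primary endpoint may attend later and report earlier AEs with dates. This stands as a limit on size. It does not remove the problem, because a patient who stops attending does stop contributing AEs.

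3. **The Analysis Set removes some drop-outs.** It does, and the gap falls accordingly. With a single early visit sufficient for entry, it would remove all of them only if none attended V1, V2 or V3.

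4. **Attribution belongs to the SAP.** Section 9.3.3 leaves the rules defining groups to the SAP, and Section 8.2 records relationship to treatment. A reader might infer that add-on complications will be charged to the conservative group and waiting-period reactions to the invasive group. The protocol keeps add-on patients in the conservative group for endpoint 2 but does not say so for AEs, so that reading is not established. A group rule alone would not, however, correct unequal observation time. Nor can V-i be counted as always an extra AE visit for the invasive group: the note to Table 1 has it replace an overlapping visit.

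5. **Patient-year rates have their own weakness.** A single 24-month rate assumes a roughly constant hazard and would dilute AEs that cluster after a procedure. This stands, and is why cumulative incidence should lead. The illustration above makes the same constant-hazard assumption.

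**Conclusion.** The point holds in a conditional form. As written, the protocol would put side by side two AE percentages that can rest on different observation times, with the bias favouring the group expected to lose more patients. With equal true hazards of 0.1 to 0.6 per year, the illustrative gap is about 3 to 20 points if all drop-outs remain in the Analysis Set, shrinking towards zero as more of them leave before any V1 to V3 visit.

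The size rests on the assumed hazards, on the timing of drop-out and on drop-out ending AE observation. The direction also assumes that the share of drop-outs with no V1 to V3 visit is similar in the two groups. It would be too strong to say that the AE figures will mainly reflect observation time: a calculation that sets the hazards equal cannot show what share of an observed difference is artefact. How far AEs would be misattributed between treatments depends on group rules left to the SAP. The change is worth making because it is cheap and uses dates already collected.

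**What to change.** In Sections 4.3 and 9.3.3:

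- Keep the number and proportion of patients with AEs.
- Add the cumulative incidence of first treatment-emergent AE, as already defined in Section 8.1, at 12 weeks, 12 months and 24 months from the start of the treatment concerned, censored at last contact.
- Add treatment-emergent AEs per 100 patient-years as support, split by period where possible so that early procedural events are not averaged over the whole follow-up.
- Tabulate AEs by treatment received at onset: before the intervention, on conservative treatment, after the first intervention, and after an add-on or re-intervention.

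**Cost.** Wording in two sections and some programming. No new data are needed, and Section 9.3.3 already plans Kaplan-Meier methods for its time-to-event endpoints. The safety tables become slightly longer, and AEs with partial dates need an allocation rule. Censoring at last contact assumes that leaving is unrelated to AE risk, which should be stated beside the result.

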### **Complementary analysis**

There is a possibility of carrying out complementary analyses at the end of the study according to the data obtained if they allow this type of analysis.

### **Interim analyses**

Not applicable

## 10. Quality assurance

### 10.1 Study Monitoring

In accordance with applicable regulations, Good Clinical Practice (GCP), and Contract Research Organisation (CRO) Standard Operating Procedures (SOPs), an initiation visit will be performed remotely (by session of 5 GPs) before any patients are included in the study. The aim of this visit is to train the investigator on the protocol and data collection procedures as well as to provide a reminder of the investigator responsibilities according to ICH GCP.

During the study, the Clinical Research Associate (CRA) will regularly contact the centres and on-site monitoring visits can be performed. The extent, nature and frequency of on-site visits will be based on the patient inclusion rate and will be discussed with the investigator. The aim of these contacts and visits is to check the progress of the study, discuss recruitment, review collected study data, conduct source document verification and identify any issues and address their resolution. This will be done in order to verify that the data are authentic, accurate and complete, the safety and rights of patients are being protected and the study is being conducted in accordance with the approved protocol (and any amendments), GCP, and all applicable regulatory requirements.

The investigator agrees to allow the CRA direct access to all relevant documents and to allocate his time and the time of the study personnel to discuss any issues.

Upon completion of the study the CRA, with the collaboration of the investigator, will ensure that:

- All data queries have been finalised,
- The centres' study records are complete.

### 10.2 Audit

To ensure compliance with GCP and all applicable regulatory requirements, the sponsor or a CRO designated by the sponsor may conduct a quality assurance audit of the investigator centre. Regulatory agencies may also conduct regulatory inspections. Such audits or inspections can occur at any time during or after completion of the study. If an audit or inspection occurs, the investigator centre agrees to allow the auditor / inspector direct access to all relevant documents and to allocate his time and the time of the study personnel to the auditor / inspector to discuss findings and any relevant issues.

## 11. Direct access to source data and documents

According to GCP guidelines, upon request of the CRA, auditor, Independent Ethics Committee (IEC) or regulatory authority, the investigator must provide direct access to all requested source data / documents. The investigator(s) and the institution(s) will permit study-related monitoring, audits, Ethics Committee (EC) review, and regulatory inspections (where appropriate) by providing direct access to source data and other documents (ie patients' case sheets, questionnaires etc). This will be defined in a written agreement with the sites.

## 12. Ethics and regulatory approvals

The study will be conducted in compliance with the principles of the Declaration of Helsinki (current version), the principles of GCP and in accordance with all applicable regulatory requirements. This protocol and related documents will be submitted for review to the EC of UZ Leuven. Any modification of the protocol will be made only with the agreement of the sponsor and must be submitted to the EC. No changes in the clinical study protocol will be implemented until the amendment and revised ICF (if applicable) have received approval from the EC.

The study can and will be conducted only on the basis of prior informed consent by the patients, or their legal representatives, to participate in the study. The participating site shall obtain a signed ICF for all patients prior to their enrollment and participation in the study in compliance with all applicable laws, regulations and the approval of the (local) EC, if required. The participating site shall retain such ICFs in accordance with the requirements of all applicable regulatory agencies and laws.

The Investigator and the participating site shall treat all information and data relating to the study disclosed to participating site and/or investigator in this study as confidential and shall not disclose such information to any third parties or use such information for any purpose other than the performance of the study. The collection, processing and disclosure of personal data, such as patient health and medical information is subject to compliance with applicable personal data protection and the processing of personal data (Regulation (EU) 2016/679 also referred as the General Data Protection Regulation ("GDPR") and the Belgian Law of July 30 2018 on the protection of natural persons with regard to the processing of personal data).

